This is a 5-year, randomized controlled trial (RCT) that aims to test a native, novel web application called "PCplanner" developed by an external technology vendor, One Cow Standing. PCplanner directly captures EHR data to automate the identification of older adults with palliative care needs based on clinical characteristics such as dementia and declining health status. The app engages families as partners in their loved one's care by facilitating in a self-report of actual needs. Additionally, the app provides a scalable digital infrastructure for coordinating needs-targeted care from collaborating ICU teams and palliative care specialists. The project specifically intends to randomize 150 older patients aged ≥50years, their 150 self-described family members, plus their ICU clinicians to determine if the intervention can improve family-reported unmet palliative care needs compared to standard of care.

Study Aims

The project will operationalize this goal by completing three specific aims, which are described below:

- Aim 1: Optimize the usability of the PCplanner mobile app, specifically for older adults.
 Approach and goal: To optimize the PCplanner mobile app platform before Aim 2's clinical trial, key features will be added, based on user testing feedback, compatible for older adult caregivers and clinicians. Iterative revisions based on usability participant feedback will be performed until the app platform achieves 'excellent' usability (i.e., mean Systems Usability Scale (SUS) score >60).
- **Aim 2**: Test the PCplanner intervention's efficacy vs. usual care in a randomized clinical trial (RCT). *Hypotheses*: Compared to usual care at 8 days post-randomization, PCplanner-augmented care will improve family-reported unmet palliative care needs. It will also improve short-term and long-term (3-month) secondary outcomes among family caregivers

Protocol Version: 5.1 Dated: 13 June 2022 Page 6 of 42

(psychological distress symptoms, quality of communication), patients (receipt of goal concordant treatment), and health systems (length of stay). *Approach and goal:* In academic and community medical center settings, the study team will test these hypotheses among the family caregivers of medical and surgical ICU patients with dementia, declining health status, poor functioning, and other characteristics common to the aging experience.

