Secondary outcomes will include family caregiver psychological distress symptoms measured with the PHQ-9 (depression),¹³ the GAD-7 (anxiety),¹⁴ and the PTSS (PTSD) at survey 3 (T3) (1 week post-randomization) and survey 4 (T4) (3 months). Systems outcomes will include post-randomization length of stay (LOS), use of aggressive care, discharge disposition, and hospice use.^{15,16} Clinicians will complete a brief palliative care attitudes scale at the time of consent.¹⁷ Aim 3's analysis of facilitators, barriers, and mechanisms will be based on transcribed semi-structured family and clinician interviews.

Study Overview Aim 1

The previous pilot showed compelling results, but also identified targets that could substantially improve app functionality. However, changes in an app's user interface or function, regardless of intention, can influence intervention delivery, data validity (e.g., ePRO system), as well as *usability*—the quality of the user's experience across domains of ease of use, efficiency, memorability, error rate, and

Protocol Version: 5.1 Dated: 13 June 2022 Page **7** of **42**

satisfaction.¹⁸⁻²⁰ Usability testing is a critical procedure because it can identify any problems proactively, using lessons learned to improve the software before its introduction in a clinical trial setting.^{1,19,21} Therefore, Aim 1, a cross-sectional refinement (*not* developmental) study involving 10-15 participants, will aim to improve efficiency, memorability, satisfaction, and overall decrease error rate. Participants eligible for this portion of the study will be healthy volunteers, specifically Duke employees, at least 18 years of age or older. Aim 1, completed concurrently with Aim 2 startup tasks, will target three key areas:

- Engagement and personalization: the study team will enable a 'Recommender System' to improve user experience including reminders and notifications, dashboard views unique to study role (e.g., CRC vs. clinical teams), enhanced visualization of needs data, single-click ICU team approval for study team members to approach families, and hovering box feedback in response to user-completed tasks.
- 2. Security: The Duke Health Technology Support team will ensure that the app system's security adheres to current standards throughout the course of the trial.
- 3. Interoperability: Standards will be used for EHR triggers with the assistance of DHTS ACE team programmers.

Aim 2

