At each specified time point above, the study team will abstract, as needed, relevant clinical data, as defined in the study EDC manual of procedures (MOP) and enter into the EDC, REDCap.

Compensation

Compensation for study participation will be provided to each family member via Greenphire. Participants may receive up to a total of \$60 for study completion:

- T1: \$15.00
- T2: \$15.00
- T3: \$15.00
- T4: \$15.00

Compensation for study participants in aims 1 and 3 will also be provided. Participants who partake in aim 1 or 3 will receive a one-time payment of \$15.00 for the completion of the single study visit.

6. Subject Participation Duration: For those subjects enrolled in Aims 1 and 3, we anticipate their study participation consisting of only one study survey, which will last for 30-60 minutes. For the RCT (Aim 2), it will require 3 months for participants to complete the entire study from the time of randomization, including the intervention and all the follow up surveys.

7. Enrollment sites

This study will be conducted at Duke University Health (DUH), Duke Regional Hospital (DRH), and Duke Raleigh Hospital—all sites within the Duke University Health System.

8. Statistical Design, Analyses, Sample Size and Power Statistical Design and Analyses Plan *Aim 1*

Protocol Version: 5.1 Dated: 13 June 2022 Page 14 of 42

After programming is complete, the study team will determine PCplanner usability using a 'system-user-task-environment' mixed-methods approach. The study team will interviews with healthy volunteers to determine app usability. During the single 30-minute sessions participants will complete: a 'think aloud' protocol in which CRCs record comments as PCplanner is used; a semi-structured interview, and the 10-item (0 [lowest] to 100 [highest]) industry-standard Systems Usability Scale (SUS). App revisions that address the needs of all users. The study team anticipate 2-3 cycles of 5-10 users each will achieve our testable hypothesis that PCplanner will attain a mean SUS score >60 ('excellent' usability). 33,34

Aim 2

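### Aim 1 uses an observed mean SUS above 60 both to end app revisions and as its hypothesis, and its two participant ranges differ (10-15 against 10-30)

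*Combined protocol and SAP*

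**What the plan says.** Three places in the combined protocol and SAP bear on this.

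- **Section 3, Study Aims, Aim 1** gives the stopping rule: revisions based on user feedback continue "until the app platform achieves 'excellent' usability (i.e., mean Systems Usability Scale (SUS) score >60". No maximum number of cycles is stated, nor what happens if the threshold is never reached.
- **Section 8, Statistical Design, Aim 1** gives the same threshold the status of a hypothesis. The team expects that "2-3 cycles of 5-10 users each will achieve our testable hypothesis that PCplanner will attain a mean SUS score >60". Each user attends one 30-minute session. No SD, null value, error rate or confidence interval is given, and the text does not say whether the mean is taken per cycle or pooled over cycles.
- **Section 3, Study Overview, Aim 1** gives the size as a "study involving 10-15 participants".

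Section 3 (Primary Outcomes) lists the SUS for usability together with interview analysis, and the CSQ-8 for acceptability. Section 5 (Compensation) pays Aim 1 participants once, for a single visit.

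**The concern.** Stopping revision when a target is reached is a sound development rule. The difficulty arises when that stopping event is also reported as a hypothesis that was met. The threshold is applied to an observed mean, possibly from as few as 5 users, and the text allows revision and retesting until it is passed. An app version whose true mean is below 60 can then be reported as having met the hypothesis, and the mean that triggered the stop will tend to overstate usability. The SUS is part of the Aim 1 primary outcome and describes the app carried into the trial, so the figure is likely to be quoted as a result.

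The second issue is simpler. Two sections give different participant ranges for the same aim.

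**Working it through.** **Participant range.** Each user is seen once (section 8 Aim 1; section 5 Compensation), so participants = cycles × users per cycle.

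- Smallest: 2 × 5 = 10. Largest: 3 × 10 = 30.
- The Study Overview's 10-15 is reproduced only with 5 users in every cycle: 2 × 5 = 10 and 3 × 5 = 15.
- With equal cycles, only 2 cycles of 5, 6 or 7 users (10, 12, 14) or 3 cycles of 5 (15) stay within 15. Two cycles of 8 (16) or three of 6 (18) exceed it. Unequal cycles such as 5 + 10 = 15 also fit.
- The lower ends agree. The upper end implied by section 8 is twice the stated one.

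**Repeated looks at the threshold.** The plan has no figure here to reproduce. From the documents: threshold 60, 5-10 users per cycle, 2-3 cycles. Assumed, because the documents are silent: SUS SD 12-20, normally distributed cycle means, the mean judged cycle by cycle, and a true mean that revisions do not change.

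- One cycle: p = 1 − Φ((60 − μ) / (SD/√n)).
- At least one pass in k cycles: 1 − (1 − p)^k.

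With μ = 55 and n = 5:

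- SD 12: standard error 12/√5 = 5.37, z = 5/5.37 = 0.93, p = 0.176. Three cycles: 1 − 0.824³ = 0.44.
- SD 20: standard error 20/√5 = 8.94, z = 5/8.94 = 0.56, p = 0.288. Three cycles: 1 − 0.712³ = 0.64.

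| True mean | Users per cycle | One cycle passes | At least one of three passes |
|---|---|---|---|
| 55 | 5 | 18-29% | 44-64% |
| 55 | 10 | 9-22% | 26-52% |
| 50 | 5 | 3-13% | 9-35% |
| 60 | any | 50% | 87.5% |

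With no cap, 1 − (1 − p)^k tends to 1 for any p above zero. At a true mean of 60 it is 96.9% after five cycles and 99.9% after ten.

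**Upward selection.** The expected mean of a passing cycle is μ + SE × φ(z)/(1 − Φ(z)). For μ = 55 and n = 5 this is 62.9 (SD 12) to 65.6 (SD 20), about 8 to 11 points above the true value.

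**Precision of one cycle.** The 95% half-width is t × SD/√n.

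- n = 5: 2.776 × 5.37 = 14.9, to 2.776 × 8.94 = 24.8.
- n = 10: 8.6 to 14.3.

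An observed mean of 61 from 5 users therefore has a lower limit between 61 − 24.8 = 36.2 and 61 − 14.9 = 46.1.

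**The case against.** The strongest reply is that Aim 1 is formative. It refines an existing app with employee volunteers, uses think-aloud sessions and interviews as well as the SUS, and claims no p-value or error rate. This stands as a limit on importance, and it is a reason to change the label rather than to demand a confirmatory study.

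A reader might infer that the hypothesis can hardly fail. The documents do not support that in general. It follows only if the revision rule in Study Aims is uncapped. If the 2-3 cycles in section 8 are a limit, then at a true mean of 55 with three cycles of 5 users, 36-56% of such programmes would still fail.

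The pass rates also rest on assumptions that raise them. Revision is meant to improve the app, and where it does, a later pass is more often deserved. If 15 users were pooled and judged once, a true mean of 55 would pass only about 5-17% of the time (SD 12-20). The text permits that reading because it does not say how the mean is formed. These points limit the size of the effect. They do not change the fact that one event serves as both stopping rule and hypothesis.

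On the participant range, the two statements overlap and section 8 only states an expectation. That makes it a mismatch at the upper end rather than a complete contradiction.

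**Conclusion.** The point holds in limited form. Under the uncapped wording, reaching a mean SUS above 60 is the only recorded way for revision to end, so it cannot also test a hypothesis. Under a cap of three cycles failure is possible, but the pass rate at a true mean of 55 rises from 18-29% to 44-64%. That comparison assumes 5 users per cycle, per-cycle means, SD 12-20 and no real improvement, so it illustrates an unfavourable case and does not forecast the result. The participant ranges conflict at their upper ends (15 against 30) without any assumption beyond one session per user, which the documents state.

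A reader might also infer that the trial itself is weakened. It is not: no Aim 2 sample size, error rate or primary analysis uses the SUS result.

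**What to change.** 1. In section 8 (Aim 1), replace the hypothesis wording with a go/no-go development target of mean SUS >60. State the maximum number of cycles, how the mean is formed, and what happens if the target is not met.
2. Report the mean SUS of the final app version, from the users who tested that version, with its 95% CI. Show every earlier cycle's mean beside it, because an interval from the cycle that triggered stopping does not by itself remove the selection. Do not claim that true usability exceeds 60 unless the interval supports it.
3. Give one participant range in the Study Overview and in section 8: either 10-15 (2-3 cycles of 5) or 10-30 (2-3 cycles of 5-10).

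The cost is protocol wording. Choosing 10-30 would add at most 30 − 15 = 15 volunteers, or 15 × $15 = $225 in payments. The downside is a wider and less favourable stated Aim 1 result. A separate test cycle of 5 users is not needed for this fix, and it would still carry a half-width of about 15-25 points.

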• Aim 3: Explore family caregiver and clinician RCT experiences to characterize how these participants may have been impacted by intervention components in a variety of implementation contexts, with a goal of understanding intervention mechanisms and barriers to future implementation and dissemination. Approach and goal: Using a mixed methods approach, we will integrate findings from both qualitative analysis of semi-structured interviews via telephone with family caregivers and clinicians as well as quantitative family caregiver, patient, and care process outcomes. This will provide insight into mechanisms of action and highlight methods for future intervention optimization through enhanced personalization, replicability, and scalability—all factors that are critical to successful implementation and dissemination of the intervention.

Primary and Secondary Outcomes

All outcomes have been piloted by the Duke University study team and chosen based on the conceptual model, expert recommendations, and psychometrics (Table 1).²⁻⁴ Response burden will be minimized with short instruments and online data entry via ePRO.⁵ Pilot testing confirmed completion in 15-20 minutes and demonstrated that all outcomes were responsive at levels of clinical significance.¹ Data will be collected at pre-randomization baseline (T1 Data Collection) as well as 4 days (T2 Data Collection), 8 days (T3 Data Collection), and 3 months (T4 Data Collection) post-randomization.

Primary Outcomes

For Aim 1, usability will be assessed with the SUS ⁶ and analysis of semi-structured interview transcriptions, while acceptability will be measured with the Client Satisfaction Questionnaire (CSQ-8).⁷

For Aim 2, the primary RCT outcome will be unmet palliative care needs at T3 (8 days post-randomization) as reported by family caregivers using the Needs; Existential concerns; Symptoms; and Therapeutic interaction (NEST) scale.^{1,8,9} The NEST, which assesses palliative care needs among both critically ill older adult patients and their family caregivers (and is completed by family caregivers), is the primary trial outcome and T3 is the primary timing of its measurement.⁹ The NEST's 13 items (score range 0-130) sample each of the National Consensus Project's eight domains of palliative care quality.¹⁰ The main patient-level outcome will be the receipt of goal concordant care at T2.^{11,12}

Secondary Outcomes

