We will test the primary study hypothesis that the NEST score is lower (i.e., fewer unmet needs) for intervention family caregivers compared to usual care at T3 (~1-week post-randomization). All participants will be analyzed as part of the group they were assigned, regardless of adherence or crossover status (i.e., intention to treat). We will use a general linear model to estimate mean NEST changes and corresponding confidence intervals over time using SAS PROC MIXED (SAS Institute, Cary NC). Different correlation structures will be examined (e.g., unstructured, autoregressive) and model fit indices will be used to guide the choice of the final model's structure.

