Analyses similar to those conducted for the NEST (primary outcome analyses) above will be performed for the secondary family caregiver hypotheses involving PHQ-9, GAD-7, and PTSS scores at T3 and T4. While family caregivers will be interviewed at T4 regardless of patient survival, patient death could complicate the analyses in two key ways: (1) Presence of missing data due to family loss to follow up (i.e., non-random missing data) and (2) differences in family caregiver distress by patient survival status (i.e., heterogeneous effect). 35 To address the impact of patient death on outcomes, after first exploring reasons for and predictors of dropout, we will conduct a 2-step supplemental analysis. In Step 1, missing T4 data due to loss to follow up among family caregivers of survivors will be multiply imputed via SAS PROC MI. In Step 2, we will account for T4 outcomes that are missing due to death via composite endpoint and principal stratification methods to estimate the causal effects of the intervention in the presence of these unidentified outcomes and complicated missing data patterns. 36,37 For the key patient outcome, receipt of goal concordant care, we will use logistic regression models adjusting for the stratification variables, to examine if rates at T3 differ by treatment group. The key healthcare systems outcome, post-randomization hospital length of stay (LOS), provides a unique challenge due to the high expected mortality rate (40-50%). In addition to descriptive analyses, steps to examine treatment group LOS differences will include: (1) a proportional hazards model with death treated as a censoring event; (2) a chi-square test of mortality rate differences; and (3) a Brunner-Manzel rank test for the composite death-LOS outcome. This last step implements a recently developed methodology of a composite outcome that incorporates a numerical value for death (i.e., coded as the worst possible outcome or the longest possible stay) in the observed LOS distribution. 38,39

Aim 3

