Duke: Call Emergency Psychiatry at [contact] or [contact], available 24 hours a day, 7 days a week.

Protocol Version: 5.1 Dated: 13 June 2022 Page 18 of 42

• The National Suicide Prevention Lifeline - [name] is a free, 24-hour hotline available to anyone in suicidal crisis or emotional distress.

As described above, all concerns about participant safety will be discussed immediately with the PIs - including concerning severe distress that does not involve suicidality.

For these situations, once an "alert situation" is known, the PIs will refer the participant if needed (based on a PI-led phone call) to local psychological resources. The study team will also make urgent and emergency referrals as needed based on information learned.

To date, in previously completed similar studies, analysis has found that <5% of participants will require a call from the study team during some point in the study period. Of those, none have required referral to acute psychiatric care after a detailed interview from the study team. After a disposition/solution has been made, both the resolution (and follow up) will be documented in the 'contact log' section of the data system for reporting to the DSMB.

Patient Death While in Study

Finally, it is recognized that this project targets patients who are critically ill and elderly, therefore, there is a risk of death. The study team will review the EMR to look for records of death, halting all study procedures, if applicable, and noting the date of death. Additionally, on phoning any family member, the study team will initiate a conversation to tactfully ascertain the patient's vital status. If the patient has died, we will provide brief support. If a family member states that they wish to drop out, the study team will respect that as well. A follow-up question may be asked to ascertain the reason for withdraw; however, this is for documentation purposes only.

Vulnerable Populations

The study team not enroll patients from vulnerable populations (e.g., imprisoned persons, minors). However, elderly patients will be targeted for enrollment into this project, and therefore, there is a potential risk of death due to their age and critical illness in < 3 months.

Potential Benefits

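### The plan's imputation and death analyses for caregiver outcomes stop at T4, so the primary T3 NEST rests on an unstated, untested missing-at-random assumption, and T3 collection after a patient's death is left unclear

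*Combined protocol and SAP*

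**What the plan says.** Section 3 (Primary Outcomes) states that "the primary RCT outcome will be unmet palliative care needs at T3 (8 days post-randomization) as reported by family caregivers". The caregiver completes the NEST, but the scale "assesses palliative care needs among both critically ill older adult patients and their family caregivers".

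Section 8 (Aim 2) gives the primary analysis: "We will use a general linear model to estimate mean NEST changes and corresponding confidence intervals over time using SAS PROC MIXED". It adds a choice among correlation structures and intention to treat: "All participants will be analyzed as part of the group they were assigned, regardless of adherence or crossover status". It does not mention missing T3 scores, patient death before T3 or any sensitivity analysis of the primary result.

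The next paragraph of section 8 turns to PHQ-9, GAD-7 and PTSS. It says that patient death may cause non-random loss of caregiver data and sets out two steps. In the first, "missing T4 data due to loss to follow up among family caregivers of survivors will be multiply imputed via SAS PROC MI". In the second, "we will account for T4 outcomes that are missing due to death via composite endpoint and principal stratification methods". Follow-up irrespective of patient survival is promised there for T4 only. Appendix 5 schedules NEST at T1, T2 and T3, but not at T4.

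On learning of a death, section 10 (Patient Death While in Study) has the team "halting all study procedures, if applicable, and noting the date of death". Section 4 excludes patients who die before T1 is completed; deaths between T1 and T3 stay in the trial.

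**The concern.** The plan names a threat to its caregiver data, prescribes remedies, and leaves the primary endpoint outside them. Neither step can reach NEST, because both address T4 and NEST ends at T3.

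There are two separate gaps.

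- **Scores missing because the patient died.** A likelihood fit in PROC MIXED is valid if, given arm and the observed T1 and T2 scores, missing T3 scores behave like observed ones. When death falls after T2, both earlier scores precede it and cannot carry its effect on need. The plan neither states this assumption nor tests it.
- **Scores given after the patient died.** Some of what the NEST measures concerns the patient. No rule says how that content is scored once the patient is dead. Section 12 (Quality Assurance and Confidentiality) says that the platform forces answers to primary-outcome surveys, so a bereaved caregiver may have no way to leave such items blank.

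At stake is possible bias in the primary estimate. Section 8 expects mortality of 40-50%, without a stated time horizon. Section 12 (Data Safety Monitoring Board) allows that mortality could be higher under the intervention through decisions about life support, so the share of missing scores could differ by arm.

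**Working it through.** **1. The plan's own figure.** Section 8 (Sample Size and Power) gives SD 21.1, correlation 0.64, difference 8.80, 65 per arm and 80% power. Alpha of 5% is stated in the PHQ-9 sentence; I take it as two-sided.

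- SD of change = 21.1 × √(2 × (1 − 0.64)) = 17.90.
- Detectable difference = (1.960 + 0.842) × 17.90 × √(2/65) = 8.80.
- Power at 65 per arm = 80.0%.

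The sample-size arithmetic reproduces. The 150 randomised leave 150 × 0.9 = 135 after 10% loss, and tolerate (150 − 130)/150 = 13.3% loss before falling below 130. Death is not mentioned as a source of loss.

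**2. Reach of the death and missing-data text.**

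| Outcome | Missing-data or death analysis stated in section 8 |
|---|---|
| NEST at T3 (primary) | None |
| PHQ-9, GAD-7, PTSS at T4 | Imputation; composite and principal stratification |
| Hospital length of stay | Hazards model censoring at death; mortality test; death-LOS rank composite |

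**3. Illustrative power.** No day-8 death rate is given. Assume that a share d of patients die before T3, that all their families lack T3, and that 10% other loss applies on top. Then n per arm = 75 × 0.9 × (1 − d), and power = Φ(8.80 / (SD × √(2/n)) − 1.96).

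| d | n per arm | Power, change score (SD 17.90) | Power, baseline-adjusted (SD 16.21) |
|---|---|---|---|
| 5% | 64.1 | 79.5% | not computed |
| 10% | 60.8 | 77.3% | about 85% |
| 25% | 50.6 | 69.6% | about 78% |

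The adjusted SD is 21.1 × √(1 − 0.64²) = 16.21. The plan does not say whether the model adjusts for or constrains baseline.

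**4. Illustrative bias.** Let m be the share of an arm whose T3 is missing because of death, and k the amount by which those true scores exceed the model's prediction (1 = intervention, 0 = control). The true arm difference exceeds the missing-at-random estimate by m₁k₁ − m₀k₀. A positive value means that the model overstates the benefit.

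- Equal shares and equal k: 0.
- 15% against 10%, k = 20 in both: 0.15 × 20 − 0.10 × 20 = 1.0 unit, 11% of 8.80.
- 15% in both, k = 20 in the intervention arm only: 0.15 × 20 − 0 = 3.0 units, 34% of 8.80.

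The values of m and k are assumptions. No planned analysis would show which case applies.

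**The case against.** The strongest reply is that bereaved caregivers are meant to stay in. The caregiver is the main research subject, every family member is asked for all four surveys, only death before T1 excludes, and analysis is by intention to treat. Section 10 goes on to describe calling families, offering support after a death and respecting a wish to leave, which reads as continuation by default. The halt is also qualified. This stands in part: the text may already permit T3 after death. It does not say so, and the explicit promise covers T4 only.

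A reader might infer that the plan deletes the sickest families, or fills their T3 from families of living patients. The documents do not support that. PROC MIXED keeps bereaved families' T1 and T2 scores and conditions on them, and any T3 they provide enters directly.

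A reader might also infer that death is ignored everywhere outside T4. It is not; length of stay has its own handling.

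Nor do the documents show that the trial is underpowered. At 5% deaths power is essentially as planned. The 10% dropout may already include loss after death, and baseline adjustment would recover much of the rest.

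Finally, one might want death before T3 ranked as the worst NEST result. That would change the estimand and discard scores obtained from bereaved caregivers. It also sits badly with section 12, which says that more decisions to forgo life support could be acceptable if they reflect patient-centred care.

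The Appendix 1 workflow and the Appendix 4 figure could not be read, and the operating manual is separate. Any of them might hold a rule on surveys after death. That would answer the collection question, but would not by itself supply a T3 sensitivity analysis.

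**Conclusion.** The concern holds in a limited form. The primary T3 NEST estimate depends on a missing-at-random assumption, given T1 and T2, that the plan neither states nor tests, although section 8 itself calls death-related loss non-random. Sections 8 and 10 conflict on data collection after death, or at least leave T3 unsettled. This goes beyond missing detail: applying the halt to surveys would lose primary-outcome data for a reason linked to the outcome.

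The size cannot be fixed from the documents. Power of 79.5% to about 70% requires 5% to 25% deaths by day 8, every bereaved family lost, and 10% other loss on top. Bias runs from zero to a few NEST units, depending on arm differences in death and in unobserved need. These figures justify a sensitivity analysis; they do not predict the result. The change should be made, and settled before unblinding.

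**What to change.** 1. **Protocol, sections 8 and 10.** Reconcile the two: seek T2 and T3 from every randomised caregiver whether or not the patient has died, unless the caregiver withdraws, and limit the halt to patient-level procedures. T2 matters because Appendix 4 makes the T3 window contingent on T2 completion.
2. **Scoring.** State how patient-need content of the NEST is scored when the patient has died before the survey.
3. **Analysis.** Keep PROC MIXED as the primary analysis and state its missing-data assumption. Pre-specify a T3 NEST sensitivity analysis: multiple imputation with patient death by T3 as a predictor, and a delta shift, varied by arm, for missing scores of bereaved families.
4. **Optional.** Extend the principal-stratification or composite methods of section 8 to T3, as supportive analyses only. Ranking death as worst should not be required.
5. **Reporting.** Give deaths before T3, and T3 completion by arm and patient survival status.

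The cost is a few sentences of protocol and SAP text, one additional pre-specified analysis, and survey follow-up of bereaved caregivers. The sample size does not change.
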